8. PRIMARY ENDPOINT ANALYSES

When the use of descriptive statistics to assess group characteristics or differences is required, the following methods will be used: for categorical variables, the number and percent in each category; for continuous variables, the mean, median, standard deviation, quartiles and range (minimum, maximum). Within-treatment group assessment of the change from the baseline measurement to a follow-up measurement will be analyzed using McNemar's test (for categorical response variables) or the paired t-test or Mann-Whitney U test (for continuous variables).

To assess the adequacy of the randomization, participant's baseline characteristics including demographics and laboratory measurements will be compared between the two study arms using descriptive statistics. Due to the small sample size, formal comparisons will not be done.

8.1 Pharmacokinetic Primary Endpoint

The proportion of participants with detectable drug levels in the active arm and the measured drug concentration levels will be summarized using descriptive statistics and graphics. Concentration of TFV will be summarized for plasma, cervicovaginal fluid (CVF), rectal fluid, and cervical tissue (biopsy) biological sample types and of TFV-DP concentrations in cervical tissue. Cervical tissue is collected at two time points: Participants are randomized to biopsy collection either at Visits 5 and 8 or Visits 6 and 9. Because of the limited time points per participant, not all the following described analyses will be possible for cervical tissue concentrations.

For concentrations of TFV that fall below the corresponding assay's lower limit of quantification (LLOQ), we will use a value equivalent to half the LLOQ. For CVF, rectal fluid and cervical tissue, the assay-level LLOQ will be adjusted for the sample weight to derive a weight-normalized LLOQ for each specimen sample.

The time to each sample collection will be calculated using the time of insertion of the first IVR at Enrollment, as recorded in the Ring Insertion and Removal eCRF, and the time of sample collection, as recorded in the PK results dataset from the Lab Data Management group.

TFV concentration in the sample types will be described using the following PK parameters: maximum observed concentration (C_{max}), area under the concentration-time curve ($AUC_{0-92\text{days}}$) from enrollment until the last collected sample (Day 92), and time to maximum observed concentration (T_{max}). AUC will be calculated using the trapezoidal method² on the observed times to sample collection. The geometric

mean, geometric coefficient of variation (CV%), median, interquartile range (IQR), minimum, and maximum will be reported for these PK parameters. The CV% will be calculated as $100 \times \sqrt{\exp(s^2) - 1}$, where s is the SD of the natural log-transformed values. The natural log transformation of the concentration values will be used. In addition, these same summary statistics will be used to describe TFV concentrations at each sample collection time-point.

The following tables and figures will be generated:

- Summary table of PK parameters by site and overall
- Summary table(s) of PK concentrations for each sample collection time point and sample type by site and overall
- Spaghetti plot of PK concentrations with all participants over time for each sample type.
- Plot of geometric mean PK concentrations with bars to indicate the exponentiated mean +/- SD of the log values over time for each sample type.

8.2 Safety Primary Endpoint

For the analysis of the primary safety endpoints, two tables summarizing the number and the proportion (in percentage) of participants experiencing (i) a grade 2 or higher genitourinary adverse event and (ii) a grade 3 or higher adverse event, will be produced. Each participant will contribute once in each category (i.e., only the highest severity AE for each participant) for the calculation of the proportions. Exact 95% binomial confidence intervals for the proportion of participants experiencing each safety endpoint, using the Pearson-Clopper method, will be provided for each arm. The Fisher's exact test will be used to test for differences in event rates between the TFV IVR arm and the placebo IVR arm.

Additionally, the following listings and tables of AEs will be presented. No formal statistical testing will be conducted:

- A cumulative listing of AE sorted by arm, site, and participant ID.
- Number and percentages of adverse experiences by body system/MedDRA preferred term and severity overall and by arm, and by site.
- Number and percentages of adverse experiences by body system/MedDRA preferred term and relationship to study product overall and by arm, and by site.
- AE summary: the total number of adverse experiences by severity and relationship to study product, overall and for each arm and each site separately.

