### **Safety Analysis**

All visits in which a woman has been exposed to the study product will be included in the primary analyses of safety. Secondary intent to treat analyses may also be performed. To assess genitourinary safety, the number and the percentages of participants experiencing each safety endpoint (see [Section 10.2](#)) will be tabulated by study arm. Each participant will contribute once in each category (i.e., only for highest severity AE for each

participant) for the calculation of event rates. Exact binomial confidence intervals will be calculated for each safety endpoint for each arm and Fisher's Exact test used to test for differences in event rates between the drug containing IVR arm and the placebo IVR arm.

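### SAP 8.2's supporting adverse-event tables count events with no stated denominator, so women per arm with a given term, or with any product-related event, are not tabulated

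*SAP*

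**What the plan says.** SAP 8.2 has two parts that use different units.

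- **Primary endpoints.** The plan is for "two tables summarizing the number and the proportion (in percentage) of participants experiencing" each of two composites: genitourinary AEs of Grade 2 and above, and AEs of any kind of Grade 3 and above. The counting rule is explicit: "Each participant will contribute once in each category (i.e., only the highest severity AE for each participant) for the calculation of the proportions". This is followed by exact intervals by arm and Fisher's exact test.
- **Supporting output, without formal testing.** There are four items. The first is a listing, with no summary by arm: "A cumulative listing of AE sorted by arm, site, and participant ID". The second is a table by term and grade, and its unit is the event: "Number and percentages of adverse experiences by body system/MedDRA preferred term and severity overall and by arm, and by site". The third has the same layout, with relatedness in place of grade: "Number and percentages of adverse experiences by body system/MedDRA preferred term and relationship to study product overall and by arm, and by site". The last gives event totals only, in shortened form here: "AE summary: the total number of adverse experiences by severity and relationship to study product". The once-per-participant rule is not repeated for any of them, and no denominator is given for the percentages.

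Elsewhere the SAP names its unit: women for product holds (10.1), participant-visits for pelvic findings (10.3), and participants by reason for stopping product (6.3). SAP 3.1 defines the safety set as participants who had a ring inserted at any time.

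**The concern.** In a Phase 1 ring trial, the natural descriptive safety question is how many women on each ring had a particular symptom or finding, and how many had anything judged related to the product. An event count does not answer this directly. A woman with four episodes contributes four times, and with 32 women on TFV and 16 on placebo the raw counts differ by allocation alone.

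The two primary tables do count women, but only for their composites. A Grade 1 event of any kind, or a Grade 2 event that is not genitourinary, enters neither. Low-grade local effects can matter here. Protocol 2.4.3 describes an earlier trial of a TDF ring (a different product) that stopped early because 8 of 12 women on active ring developed Grade 1 ulceration, and Protocol 13.4.1 lists vaginal and cervical ulceration among possible side effects. A similar Grade 1 signal in MTN-038 would be summarized as an AE only in the event-based tables.

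**Working it through.** **1. The unit in each planned table that touches AEs**

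| Planned output | Unit | By preferred term? | By relatedness? |
|---|---|---|---|
| SAP 8.2, two primary tables | participants | no | no |
| SAP 8.2, term by severity | events, denominator unstated | yes | no |
| SAP 8.2, term by relationship | events, denominator unstated | yes | yes |
| SAP 8.2, AE summary | total events | no | yes |
| SAP 8.2, AE listing | one line per event, not a summary | yes | recoverable by hand |
| SAP 6.3, product discontinuation | participants, AE as one reason | no | no |
| SAP 10.1, product holds | women | no | no |
| SAP 10.3, pelvic findings | participant-visits | by type of finding | no |

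No row combines participants as the unit with preferred term or relatedness.

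**2. The plan's own safety figures are per participant.** Protocol Table 15 gives 0.97 for seeing at least one affected participant among 32 at a true rate of 10%. Check: 1 − 0.90^32 = 1 − 0.034 = 0.966, which agrees. These operating characteristics apply to counts of women, which the supporting tables do not give.

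**3. What an event count leaves open.** Arm sizes of 32 and 16 are from Protocol 10.1. The event counts are assumed: 8 events of one term among 40 TFV-arm AEs, and 4 among 20 placebo-arm AEs. The printed percentage depends on the denominator chosen:

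- AEs in the arm: 8/40 = 20% vs 4/20 = 20%
- participants in the arm: 8/32 = 25% vs 4/16 = 25%
- all AEs in the trial: 8/60 = 13% vs 4/60 = 7%, which only mirrors the 2:1 allocation

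Both of the following fit those event counts (Clopper-Pearson 95% intervals, two-sided Fisher test):

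| Women affected | TFV | Placebo | Fisher p |
|---|---|---|---|
| Scenario A | 8/32 = 25.0% (11.5 to 43.4) | 1/16 = 6.3% (0.2 to 30.2) | 0.24 |
| Scenario B | 2/32 = 6.3% (0.8 to 20.8) | 4/16 = 25.0% (7.3 to 52.4) | 0.086 |

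The point estimates reverse while the event row stays the same. The intervals overlap in both scenarios, and neither p-value is below the SAP's 5% level.

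**4. Effect of the denominator in the TDF ring trial.** Ulceration affected 8/12 = 67% of women on active ring. The trial recorded 70 AEs in total, so at one ulcer event per woman (an assumption) the share of all events is 8/70 = 11%.

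**The case against.** The case against has several parts, and much of it stands.

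- **The denominator is undefined, not declared to be events.** A reader might infer that the SAP commits to percentages of events. The wording leans that way, especially after the participant wording just above it, but a programmer could divide by participants. The supportable statement is that the denominator is missing and that participant counts are not promised.
- **Event counts do carry information about women.** A reader might infer that the tables could mislead whatever the true per-woman rates are. They could not: the number of events caps the number of women affected, zero events means zero women, and one event per woman gives the exact count. At one event each, the TDF ring's ulcers would print as 8 vs 0, which is a visible signal. Distortion needs recurrence that differs between arms, and the documents give no evidence that this is expected.
- **The example is constructed.** Scenario A puts all four placebo events in one woman. It shows opposite directions; it does not show opposite conclusions.
- **The data are recoverable.** With 48 participants, a count of women can be taken from the listing, and the arm sizes are known. This lowers the stakes, but a listing is not a summary by arm, and a hand count leaves the counting rule to be chosen after the data are seen.
- **There is no conflict between protocol and SAP.** The protocol's rule, "Each participant will contribute once in each category", belongs to the safety endpoints of Protocol 10.2, which are the two composites. SAP 8.2 applies it to the same two. The protocol does not require a per-term participant table.

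**Conclusion.** The point holds as a gap in the supporting safety tables. Their unit is the event, the percentage has no stated denominator, and women per arm by preferred term or with any product-related AE are not tabulated. The practical reach is mainly Grade 1 events and non-genitourinary Grade 2 events, because the primary tables already count women for the two composites.

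The size depends on recurrence. If each affected woman has one event of a term, nothing is lost beyond a division by 32 or 16. If recurrence is uneven, the same 8 vs 4 events are compatible with 25.0% vs 6.3% of women or with 6.3% vs 25.0%. Those event counts are assumed, and neither difference is statistically significant. The primary analysis is not affected. This is a cheap improvement that should be made; it does not invalidate the plan.

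**What to change.** In SAP 8.2:

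1. In both preferred-term tables, make the main column n (%) of participants with at least one AE, by arm. Count each participant once per body system and once per preferred term, at her highest grade, and as related if any such event is related.
2. State the denominator: participants in that arm who had a ring inserted, as in SAP 3.1 (planned 32 and 16).
3. In the AE summary, add a row for participants with any product-related AE, by arm. An exact interval is optional.
4. Keep event counts as a second column so that recurrence stays visible.

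The cost is a few lines of SAP text and minor table programming. No new data are needed, and the primary endpoints and their tests do not change.

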9. SECONDARY ENDPOINT ANALYSES

9.1 Adherence Secondary Endpoint

To assess participant adherence to the IVR, the proportion of participants who reported keeping the study IVR inserted at all times during the 91 days will be calculated along with a 95% confidence interval, using the exact Pearson-Clopper method, and these proportions will be formally compared using Fisher's exact test. Adherence will be calculated using the self-reported IVR outages from the Ring Adherence eCRF and clinician-reported outages reported on the Study Termination, the Discontinuation of Study Product, the Product Hold Log, and the Ring Insertion and Removal eCRFs. Clinician-initiated IVR removals for the purpose of clinical examination will be excluded from consideration during product adherence analysis.

For participants who were not fully adherent, the number, median, and IQR of the duration of self-reported removal/expulsion events will be reported. Additionally, the median and IQR of the cumulative time during the study period when the study IVR was outside the vagina will be calculated. No formal statistical comparisons will be performed.

Additional summaries of the number and proportion of participants who had the vaginal ring in place at the start of the visit, who had the ring removed at the visit, who had a ring inserted at the visit, and the reasons for removals from the Ring Insertion and Removal eCRF will be tabulated by arm. The following information collected on the Ring Adherence eCRF will be tabulated for all follow-up visits, overall and by arm: the total number of times that the participant had the vaginal ring out; the number of times that the participant had the vaginal ring out for more than 12 hours continuously (grouped in following categories: 0, 1, 2, 3 or more), the longest number of days in a row the vaginal ring was out; the number and proportion of participant visits where the ring was removed; the number and proportion of participant visits where the ring came out on its own; the number and proportion of participant visits reporting the different reasons why the vaginal ring was removed and the reasons why the vaginal ring came out on its own. No formal statistical comparisons will be performed.

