### **4.3 Secondary Endpoints**

**Adherence**

- Frequency of study IVR removal/expulsions (voluntary and involuntary) and duration without IVR in vagina (by self-report)
- IVR use initiation and persistence (whether the IVR is in place when participants come to the clinic for their study visits)

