### **Product Adherence Assessment**

Key adherence measures will be captured by CASI and by CRFs to ensure maximum confidentiality of responses. Product use information will be collected at Visit 6 (day 28), Visit 8 (Day 56), and Visit 9 (PUEV/Early Termination Visit). The questions will assess study IVR use, report of frequency of study IVR removal/expulsions (voluntary and involuntary) and duration without IVR inserted in the vagina. Clinician-initiated VR removals for the purpose of clinical examination are to be excluded from consideration during product adherence assessment. A series of questions will ask if the study IVR was out, whether it was removed or expelled, under what circumstances or conditions it was removed or expelled, and whether it was re-inserted. A combination of self-administered and interviewer-administered questionnaires will be employed to capture the above information. Study staff will provide participants with guidance on strategies to optimize recall of relevant behavioral and adherence data. This quantitative assessment will be modeled on the adherence assessment for protocols MTN-036 ([www.mtnstopshiv.org](http://www.mtnstopshiv.org)) and other previous trials of the DPV ring (MTN-013, MTN-020 and IPM 027 [<http://www.ipmglobal.org/>]). Additionally, at all visits in which a pelvic exam is performed, clinicians will assess whether the IVR is in place through visualization on speculum exam (or bimanual exam if needed) and record this assessment on a CRF.

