# 11 DATA HANDLING AND RECORDKEEPING

## 11.1 Data Management Responsibilities

Data collection tools will be developed by the MTN SDMC in conjunction with the protocol team. Quality control and data integrity are managed manually and systematically with reports and queries routinely generated and provided by the SDMC to the study sites for verification and resolution. As part of the study activation process, each study site will identify all CRFs to be used as source documents, and will submit test CASI data to confirm proper data transfer to the SDMC. Study CRF data will be entered and cleaned using the Medidata Rave EDC tool, a data management system compliant with the International Council for Harmonization (ICH), Good Clinical Practices (GCP) and US CFR guidelines for electronic data capture.

Research Triangle Institute will manage all qualitative data for the study. Qualitative data will be collected, stored and analyzed by Research Triangle Institute. Audio files from interviews conducted by qualitative analysts will be stored securely on HIPAA compliant servers. The audio files will be transcribed by an external transcription service and sent only over a secure file transfer protocol site. The transcriptionist will follow all procedures outlined in the Data Use Agreement with Research Triangle Institute. Transcripts will be stored securely on HIPAA compliant servers. The paper notes taken by the qualitative analyst during the interviews will be saved in a locked files cabinet in the Research Triangle Institute office.

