9.2 Acceptability Secondary Endpoint

To assess acceptability of the study IVR, the participants' answers to questions J2 ("Overall, how much do you like the ring?"), based on the participants' self-report by CASI at the Product Use End Visit (PUEV) or Early Termination Visit, will be used for this the primary endpoint analysis. The acceptability response is on the 10-point Likert scale and will be summarized by calculating the mean, standard deviation, median, IQR, minimum, and maximum values and 95% CI overall, and by study arm. A bar plot of scores reported for question J2, by arm, will be presented. In addition, acceptability between the active and placebo arms will be compared using the t-test or Mann-Whitney U test depending on the distribution of the data.

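### SAP 9.1 names no CASI source for adherence although the protocol captures adherence by CASI, so any ring outage reported only on CASI would be scored as full adherence

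*SAP*

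**What the plan says.** **Protocol.** The first secondary adherence endpoint (4.3 and 10.2) is the self-reported frequency of ring removals and expulsions and the time without the ring. Under Product Adherence Assessment in 7.9, the protocol states: "Key adherence measures will be captured by CASI and by CRFs to ensure maximum confidentiality of responses". On content it says: "The questions will assess study IVR use, report of frequency of study IVR removal/expulsions (voluntary and involuntary) and duration without IVR inserted in the vagina". On mode of collection it says: "A combination of self-administered and interviewer-administered questionnaires will be employed to capture the above information". This information is collected at Visits 6, 8 and 9. Section 11.1 treats CASI as a data stream separate from the CRFs entered in the electronic data capture system: sites "will submit test CASI data to confirm proper data transfer to the SDMC". Section 10.7.3 defines the adherence proportion by what participants reported, without naming an instrument.

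**SAP.** Section 9.1 fixes the sources: "Adherence will be calculated using the self-reported IVR outages from the Ring Adherence eCRF and clinician-reported outages" that are "reported on the Study Termination, the Discontinuation of Study Product, the Product Hold Log, and the Ring Insertion and Removal eCRFs". The resulting proportion gets an exact confidence interval and a Fisher's exact comparison between arms. The descriptive adherence tables in 9.1 draw on the Ring Adherence and the Ring Insertion and Removal eCRFs. CASI appears in the SAP for acceptability only: in the analysis set (3.1), in 9.2, where the response is taken from "self-report by CASI at the Product Use End Visit (PUEV) or Early Termination Visit", and in the exploratory acceptability analyses (11.3). The SAP gives no reason for leaving CASI out of adherence and no rule for answers that disagree.

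**The concern.** The protocol uses a private, self-administered route for adherence so that participants can answer in confidence. The SAP's scoring rule has no place for what comes in by that route. Whether the CASI items repeat those on the Ring Adherence eCRF or complement them, adherence data collected by CASI do not reach the endpoint. If those data include outages, the rule can only err in one direction relative to using all sources: a participant with a CASI-only outage moves into the fully adherent group. The number of removals and the cumulative time out may be understated for the same reason.

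This is a secondary endpoint, but it bears on the product's rationale. Protocol 2.2.1 and 2.4.4 attribute the failure of the daily-gel trial mainly to low adherence, and 2.1 presents a long-acting ring as a way round that problem. The confidence interval reflects sampling variation only and would not show an error of this kind.

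**Working it through.** **Step 1: the plan's own figure.** Inputs: n = 48, assumed observed adherence 75% and stated half-width 13.0% (protocol 10.4.2); exact Clopper-Pearson method (SAP 9.1).

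- x = 0.75 × 48 = 36.
- Lower limit: 2.5% quantile of Beta(36, 13) = 60.4%.
- Upper limit: 97.5% quantile of Beta(37, 12) = 86.4%.
- Half-width, from the unrounded limits: (86.36 − 60.40)/2 = 12.98 points.

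This reproduces the stated 13.0. The simple normal approximation gives 1.96 × √(0.75 × 0.25/48) = 12.25 points, so the plan evidently used the exact interval. There is no arithmetic error.

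**Step 2: the sources side by side.**

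| Source | Protocol 7.9 | SAP 9.1 adherence score |
|---|---|---|
| CASI | Named | Not named |
| CRF self-report | Named | Ring Adherence eCRF |
| Clinician or site forms | Ring-in-place check on a CRF | Four eCRFs |

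A participant is fully adherent under SAP 9.1 if none of its five eCRFs records an outage. An outage recorded only on CASI leaves that classification unchanged.

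**Step 3: effect per participant.** One reclassified participant moves the overall proportion by 1/48 = 2.1 points. In the comparison between arms, with 32 and 16 participants (protocol 6.1), one participant moves the active arm by 1/32 = 3.1 points or the placebo arm by 1/16 = 6.3 points.

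**Step 4: illustration.** Assume that 36 of 48 are fully adherent on the eCRFs and that k of those 36 report an outage only on CASI. The any-source proportion is (36 − k)/48. The values of k are assumptions, since the documents give no count or rate.

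| k | Any-source adherence | Exact 95% CI | Shift (points) |
|---|---|---|---|
| 0 | 36/48 = 75.0% | 60.4 to 86.4 | 0 |
| 1 | 35/48 = 72.9% | 58.2 to 84.7 | 2.1 |
| 2 | 34/48 = 70.8% | 55.9 to 83.0 | 4.2 |
| 4 | 32/48 = 66.7% | 51.6 to 79.6 | 8.3 |
| 6 | 30/48 = 62.5% | 47.4 to 76.0 | 12.5 |

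Six such participants would shift the estimate by nearly the whole planned half-width. One or two would shift it by well under half of it.

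**The case against.** The strongest reply is that duplicate collection is not shown. Protocol 7.9 is compatible with items divided between the instruments as well as with items asked twice. SAP 9.1 shows that the Ring Adherence eCRF already holds the number of times out, the longest time out, removal versus spontaneous expulsion, and the reasons. The outage questions may sit on that form alone, in which case no outage report is lost. This stands, and it makes the consequence conditional. It does not remove the mismatch, because the protocol says that adherence measures are captured by CASI and the SAP uses none of them.

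Three stronger readings are tempting and are not supported.

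- A reader might infer that the Ring Adherence eCRF is completed by staff, so that the answers most exposed to social desirability decide the endpoint. The SAP does not say how that form is completed. Clinician-reported outages also enter the score, and clinicians record whether the ring is in place at every visit with a pelvic examination.
- A reader might treat 75% as true adherence, apply assumed non-disclosure rates u of 20% to 50% in 1 − 0.25 × (1 − u), and conclude that the bias is 5 to 12.5 points (80% to 87.5% reported). The 75% is an assumed observed rate and the values of u come from no document. As an effect of leaving CASI out, the sum also requires that no concealed outage reaches a clinician form and that every one is disclosed on CASI.
- A reader might conclude that an outage on either instrument, with the larger count and duration, must be the primary rule. That turns recall and entry errors into non-adherence, and the documents hold no evidence on which instrument is more accurate.

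Objective markers are also planned: residual drug and total drug released (SAP 11.1 and 11.2), and plasma and CVF levels as exploratory adherence endpoints. They give context but do not enter the adherence score. Ring-in-place checks show status at a visit, not between visits.

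**Conclusion.** The point holds in a limited form. SAP 9.1 leaves out a data source that the protocol names for this measure, without a reason and without a rule for disagreement. If CASI holds outage items, an outage reported only there is scored as full adherence, at 2.1 points per participant overall. The direction is certain relative to an any-source rule: leaving a source out can raise the proportion or leave it unchanged, never lower it. The total size cannot be computed from the documents. It depends on whether CASI asks about outages and on how many participants report one there and nowhere else. The documents do not establish that confidential answers were discarded, that the reported adherence will be biased by any stated amount, or that the eCRF figure is the less accurate one. For a secondary endpoint this is a gap worth closing before the adherence analysis is run.

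**What to change.** Amend SAP 9.1 as follows.

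1. Add the CASI outage items from Visits 6, 8 and 9 as a named source. If the questionnaire holds no such items, say so, and the point is closed.
2. Report the fully adherent proportion, with its exact interval and Fisher's exact test, in two ways: by the Ring Adherence eCRF and clinician forms as now, and by any source, where an outage on CASI or on any of the eCRFs counts as not fully adherent. State in advance which of the two is primary.
3. Tabulate agreement between CASI and eCRF by arm.
4. Present counts and durations of outages by source, without automatically taking the larger value.

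Keep the existing exclusion of clinician-initiated removals for examination in both versions.

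The cost is SAP wording and the merge of a dataset that the protocol already has transferred to the statistical centre. The drawback is that some disagreement will be recall error, so the any-source figure may be somewhat too low. That is why both figures and the agreement table should be shown together.
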